9.3.2 Safety Population

The Safety population is defined as all patients who received at least 1 dose of MGCD265 and will be equivalent to the mITT population for this study. The Safety population will be used for all safety analyses.

9.3.3 Molecular Marker Evaluable Population

The molecular marker evaluable population will consist of all patients in the mITT population for whom results of gene alteration tests in tumor tissue and/or ctDNA are available.

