Sponsor-approved local test, retrospective analysis by the central tissue testing laboratory is key.

Treatment Arms C and D, based on documentation of target gene alteration using the ctDNA test, are intended to include patients for whom central laboratory tumor tissue testing fails for technical reasons, or the search for suitable tumor tissue or test results prove that none exist (to be documented in the patient records).

Individual patients with gene alterations are likely to qualify for entry into two or more treatment arms. The correlation between target gene mutations in tumor tissue and ctDNA is expected to be high. In addition, patients may have both target gene mutation and amplification. The priority for assignment to treatment arm will be in the order A to D listed above.

The Phase 2 study will use a Bayesian Predictive Probability Design ([Lee-2008](#)), applied separately and using the same assumptions in each treatment arm (see Section 9.1). Emerging tumor response data will be evaluated continuously beginning after 10 patients in each treatment arm have completed their first on-study disease assessment and are considered part of the mITT population. Stopping rules for futility are described in Section 9.1. Assuming the stopping rules are not triggered, the total sample size to be evaluated in each treatment arm of the Phase 2 study is 45 patients. The primary analysis will be conducted in the mITT (defined in Section 9.3.1).

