4 SUBJECT SELECTION AND ENROLLMENT

Patient eligibility must be reviewed and documented by an appropriately qualified member of the investigator's study team before patients are included in the study. No exceptions to the patient eligibility requirements will be granted by the Sponsor.

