4.1 Inclusion Criteria

Patients must meet all of the following inclusion criteria to be eligible for enrollment into the study:

1. Histologically confirmed NSCLC with metastatic or unresectable, locally advanced disease.
2. Receipt of at least one prior platinum-containing chemotherapy or licensed immunotherapy regimen in the advanced disease setting.
3. Molecular analysis of patient-derived samples using a Sponsor- approved method and laboratory that demonstrates a genetic alteration activating *MET* in tumor tissue and/or ctDNA. If eligibility is established using a Sponsor-approved local laboratory, a tumor tissue specimen and/or blood sample is expected to be available for retrospective sequencing in the central laboratory selected by the Sponsor.
4. Measurable disease, as per RECIST version 1.1.
5. Eastern Cooperative Oncology Group (ECOG) performance status 0, 1, or 2 (Appendix 1).
6. Adequate bone marrow and organ function demonstrated by:
 - a. Absolute neutrophil count $\geq 1,000/\text{mm}^3$ ($\geq 1.0 \times 10^9/\text{L}$)
 - b. Alanine aminotransferase (ALT) and aspartate aminotransferase (AST) $\leq 2.5 \times$ Upper Limit of Normal (ULN), or $\leq 5.0 \times$ ULN for patients with documented liver metastases. Alkaline phosphatase levels $\leq 2.5 \times$ ULN. In the presence of extensive bone metastases, there is no upper limit for alkaline phosphatase.
 - c. Total bilirubin $\leq 1.5 \times$ ULN or $\leq 3.0 \times$ ULN for patients with Gilbert Syndrome or documented liver metastases.
7. ≥ 18 years of age.
8. Women of child-bearing potential (WOCBP) or men whose partner is a WOCBP agrees to use contraception while participating in this study, and for a period of 6 months following termination of study treatment.

9. Completed informed consent process, including signing IRB/EC-approved informed consent form.
10. Willing to comply with clinical trial instructions and requirements.

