6 STUDY ASSESSMENTS

6.1 Screening

Voluntary, written, dated, and signed informed consent must be obtained before any study specific procedures are performed. Patients who completed the informed consent process but did not enroll on the study will be considered as screen failures. Limited information will be recorded in the CRF for these patients.

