9.3 Analysis Populations

9.3.1 Modified Intent-to-Treat Population

The Modified Intent-to-Treat (mITT) population is defined in each arm as all patients who receive treatment at least one dose of MGCD265 on this study.

The primary efficacy analyses of the primary and secondary efficacy endpoints will be performed in the mITT population.

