9.6.2 Gene Alterations in Tumor DNA

Tumor tissue and ctDNA genetic alterations activating *MET* will be presented descriptively, by treatment arm. Moreover, change-from-baseline in ctDNA will be presented by visit and treatment arm to assess change in genetic alteration status in ctDNA with MGCD265 treatment over time.

A concordance analysis will be conducted between target gene alterations identified in tumor tissue versus ctDNA in individual patients at prescreening/baseline. Cohen's Kappa, sensitivity and specificity will be estimated for ctDNA as well as Spearman's correlations between tumor tissue and ctDNA.

An analysis of covariance will be performed on changes in ctDNA through time including Time and Treatment as fixed effects and ctDNA at baseline as covariate.

Further details of the analyses will be presented in the SAP.

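### The tissue-versus-ctDNA concordance analysis has no named population, and the only molecular set holds MET-positive patients, so specificity and kappa would follow eligibility and arm mix

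*Combined protocol and SAP*

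**What the plan says.** Section 2.1.2 makes the correlation between tissue and ctDNA findings a secondary objective. Section 9.6.2 carries it out: "A concordance analysis will be conducted between target gene alterations identified in tumor tissue versus ctDNA in individual patients at prescreening/baseline". Besides Cohen's kappa and Spearman correlations, "sensitivity and specificity will be estimated for ctDNA". The section names no analysis set and leaves further detail to the SAP; the supplied document holds no SAP text beyond protocol Section 9.

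The only set defined for molecular data is in Section 9.3.3: "The molecular marker evaluable population will consist of all patients in the mITT population" who have tissue and/or ctDNA results. The mITT population (Section 9.3.1) is "all patients who receive treatment at least one dose of MGCD265 on this study".

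To be dosed, a patient needs a molecular analysis "that demonstrates a genetic alteration activating *MET* in tumor tissue and/or ctDNA" (Section 4.1, criterion 3). Section 4 adds: "No exceptions to the patient eligibility requirements will be granted by the Sponsor".

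Section 3 assigns patients in priority order A to D. Arms A and B are tissue-positive. Arms C and D "are intended to include patients for whom central laboratory tumor tissue testing fails for technical reasons", or for whom no suitable tissue can be found. Section 6.1 says of patients who consent but do not enroll: "Limited information will be recorded in the CRF for these patients".

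**The concern.** Specificity needs patients who are negative on the reference test, here tissue. Kappa needs both agreement cells, including the double negatives. Eligibility removes the double negatives, and the arm structure removes nearly all tissue-negative patients with a ctDNA result. A set drawn from dosed patients therefore cannot show how often ctDNA is correctly negative for MET.

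At stake is the interpretation of two of the statistics named for a stated secondary objective. The platform evaluation described in Section 1.1.4 used 10 genetic markers and gives no MET-specific figures, so this analysis is where the trial could supply them. Reported from the dosed set, a good assay could look as if it had no agreement with tissue, or its kappa could shift because one arm stopped early.

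**Working it through.** **Inputs.** Sensitivity 0.85 and specificity 0.98 (Section 1.1.4, which gives more than 85% and 98%); MET prevalence about 7% in lung adenocarcinoma (Section 1.3), varied from 5% to 10%; up to 45 patients per arm, with futility stopping possible from 10 (Section 9.1). Arm mixes and retest failure rates are assumptions.

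**Notation.** Tissue is the reference: a = tissue+/ctDNA+, b = tissue+/ctDNA−, c = tissue−/ctDNA+, d = tissue−/ctDNA−. Sensitivity = a/(a+b); specificity = d/(c+d); po = (a+d)/n; pe = [(a+b)(a+c) + (c+d)(b+d)]/n²; kappa = (po − pe)/(1 − pe). Also po − pe = 2(ad − bc)/n².

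**Plan's own figures.** None is stated for the concordance analysis. The platform figures are consistent with each other at a 7% positive share: 0.07×0.85 + 0.93×0.98 = 0.0595 + 0.9114 = 0.971, against the stated 97% accuracy. Applying 7% to that evaluation is an assumption.

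**1. Unselected benchmark, 7% prevalence.** a = 0.0595, b = 0.0105, c = 0.0186, d = 0.9114. po = 0.9709; pe = 0.07×0.0781 + 0.93×0.9219 = 0.8628; kappa = 0.1081/0.1372 = 0.79. Over 5% to 10% prevalence it is 0.75 to 0.82.

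**2. Overall MET status, arms A and B.** All pairs are tissue-positive, so c = d = 0. Specificity is 0/0. With sensitivity s, po = s and pe = s, so kappa = 0 whether s is 0.60, 0.85 or 0.95.

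**3. Overall MET status, some tissue-negative/ctDNA-positive patients included.** c > 0 but d = 0, so specificity is 0. Since ad = 0, po − pe = −2bc/n², and kappa cannot be positive. Selecting on either test positive at 7% prevalence gives a = 0.672, b = 0.119, c = 0.210; po = 0.672, pe = 0.721, kappa = −0.18. Over prevalence 5% to 10%, sensitivity 0.60 to 0.95 and specificity 0.98 to 0.999, the range is −0.02 to −0.39.

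**4. Per alteration.** Take mutation as the target, arm A as tissue-positive, and arm B as tissue-negative for mutation. The same assay gives:

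| A:B (assumed) | a | b | c | d | po | kappa |
|---|---|---|---|---|---|---|
| 45:45 | 38.25 | 6.75 | 0.9 | 44.1 | 0.915 | 0.83 |
| 45:20 | 38.25 | 6.75 | 0.4 | 19.6 | 0.890 | 0.76 |
| 45:10 | 38.25 | 6.75 | 0.2 | 9.8 | 0.874 | 0.66 |

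For 45:10, pe = (45×38.45 + 10×16.55)/55² = 0.627 and kappa = (0.874 − 0.627)/0.373 = 0.66. Specificity is estimable here, but every negative carries a MET amplification. Holding it at 0.98 assumes that these patients behave like MET-negative ones.

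**5. Central retest negatives.** Section 7.2 requests samples for later central testing from patients enrolled on an approved local test. If 2% to 10% of 90 patients in arms A and B proved tissue-negative, specificity would rest on 1.8 to 9 patients. Kappa for overall status would be 0.18 to 0.52 at specificity 0.98, and 0.08 to 0.25 at specificity 0.50, so it depends heavily on the retest failure rate.

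**6. Arms C and D.** For the qualifying alteration, any pair is ctDNA-positive by selection, so it can add only to a or c. It raises apparent sensitivity or lowers apparent specificity without testing the assay.

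**The case against.** The strongest reply is that no pooled MET status is planned. Section 9.6.2 speaks of target gene alterations, Section 2.1.2 of selected alterations, and the design treats mutation and amplification as separate targets. This stands in part. A reader might infer that specificity cannot be estimated at all, and the documents do not support that: per-alteration scoring gives a usable denominator. Nor do they support saying that kappa always reflects selection rather than the assay. At 45:45 it is 0.83, against 0.78 in unselected patients at the 6.5% prevalence in Section 1.1.3, which is a modest shift. What remains is that the scoring unit is not fixed, and that per-alteration kappa falls well below 0.83 if arm B stops early.

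Second, the link from Section 9.6.2 to Section 9.3.3 is an inference. That also stands. But no other molecular set is defined, and nothing provides for pre-screened MET-negative patients.

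Third, retesting can produce tissue-negatives, and arms C and D may yield some pairs if tissue turns up later. Both are true, so undefined or zero is exact only for the qualifying results.

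Fourth, a reader might infer that the choice of patients for arms C and D rests on this analysis. It does not: Section 1.1.4 bases it on a separate, completed evaluation of more than 150 paired samples.

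Finally, a wider pre-screened set may not exist. Section 7.2 puts tissue first, so MET-negative patients may lack a ctDNA result. Site-specific local positives are sent for central confirmation, which enriches a centrally paired set for positives. Consent may be institutional (Section 4.4). These points limit that remedy to an addition where feasible.

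**Conclusion.** The point holds as a flaw in a secondary analysis that should be corrected. On the qualifying results, overall MET status in dosed patients gives specificity of 0/0 or 0 and kappa of 0 or below (−0.18 in the central scenario), where the same assay unselected gives about 0.79. Per-alteration scoring avoids the empty denominator. Its negatives are still almost all carriers of the other alteration, and kappa runs from 0.83 to 0.66 over the assumed mixes 45:45 to 45:10.

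This rests on Section 9.3.3 being the intended set, on the Section 1.1.4 performance applying to MET, and, in the per-alteration table, on no patient carrying both alterations. Sensitivity among tissue-positive patients in arms A and B is not distorted by this selection. The primary ORR analysis and the selection of arms C and D are not affected.

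**What to change.** In Section 9.6.2, name the population and the scoring unit:

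- Score mutation and amplification separately.
- Make positive percent agreement in the tissue-enrolled arms A and B the main measure.
- Exclude arm C and D pairs from the agreement estimates.
- Drop specificity and kappa for overall MET status.
- Where consent and data allow, define an additional set of all pre-screened patients with both a central tissue and a central ctDNA result, including MET-negative patients. Estimate negative percent agreement and kappa only there, and note that the set may be enriched for positives.

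The first four changes cost only wording, in Section 9.6.2 and a matching line in Section 9.3.3. The price is that two named statistics are lost or restricted. The last needs some transfer of pre-screening data and a check of what the pre-screening consents permit; the documents do not establish that enough paired central results exist.

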9.3.4 Pharmacokinetic Evaluable Population

The Pharmacokinetic evaluable population will consist of all patients in the mITT population who had sufficient concentration-time data to permit population PK analysis for MGCD265. For patients who were noncompliant with respect to administration of MGCD265, or for patients with incomplete data, a decision as to their inclusion in the analysis will be made on a case-by-case basis.

9.3.5 Pharmacodynamic Evaluable Population

The Pharmacodynamic evaluable population will consist of all patients in the mITT population for whom PD samples are collected.

9.4 Efficacy Endpoint Definitions and Analyses

9.4.1 Objective Response Rate

Objective disease response will be categorized in accordance with RECIST v1.1 (Appendix 2). Objective Response Rate (ORR) is defined as the percent of patients documented to have a confirmed Complete Response (CR) or Partial Response (PR), as reported by the central review laboratory. The primary analysis will be conducted approximately 12 weeks after the last patient is enrolled, allowing for observation of an early disease response and confirmation of PR or CR. ORR as reported by the investigator in the CRF will be used in secondary and supportive analyses as well as by the Internal Data Monitoring Committee for purpose of decision making using the Bayesian Predictive Probability Design.

Descriptive statistics (frequency and percentage) for ORR, CR, and PR will be presented. The exact 95% confidence interval of these response rates will be constructed. An exact test for single proportion (two-sided $\alpha=5\%$) will be performed to test $H_0: ORR \leq 20\%$ against $H_1: ORR > 20\%$. Other details will be described in the SAP.

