12. Disease Evaluations: To be performed at screening (28-day window allowed) and every 6 weeks from dosing date [Cycle 1, Day 1] (-7/+10 days window allowed for first on-study assessment, ± 10 days window for all other assessments) until Week 49 (~1 year) and then every 12 weeks. All on-study disease assessments should be based on a calendar schedule beginning from the first day of dosing. In general, assessments at screening/baseline as well as on-study are to include Computed Tomography (CT) scan with contrast or Magnetic Resonance Imaging (MRI) of the chest abdomen and pelvis. In addition, at screening/baseline, a MRI with and without gadolinium or CT with contrast of the brain, a whole-body bone scan and evaluation of any superficial lesions will be performed. Subsequent disease assessments should also include whole body bone scans and/or MRI of the brain if metastatic disease is identified at screening/baseline by either the **investigator OR the central radiology reviewer**. Bone scans may be performed at one-half the frequency of other radiology evaluations (every 12 weeks) and should be performed during assessment for confirmation of disease response. All scans will be sent to the central radiology reviewer. More detailed guidance on exceptional circumstances is provided in the protocol (Section 7.3).

- 13 Adverse Events: SAEs are to be reported from the time of informed consent for study participation (i.e., excluding prescreening informed consent) until resolution of all SAEs observed on study (SAEs occurring during the screening period are only reported to the safety vendor). Adverse events will be reported from the first day of study treatment until at least 28 days after last dose of study drug, and until resolution or stabilization of acute AEs and/or ongoing SAEs. Post-treatment 28-day follow-up and beyond may be performed by remote contact (e.g., telephone call).
- 14 End of Treatment: Assessments that have been completed in the previous 3 weeks do not need to be repeated (6 or 12 weeks for tumor assessments in accordance with schedule).
- 15 Long Term Follow-up: Survival status and subsequent therapies will be collected by telephone contact every 2 months (± 14 days) from end of treatment visit until death or lost to follow-up.

Table 3: Schedule of PK, Triplicate ECG, and PD Assessments

	Cycle 1, Days 1 and 15 (± 2 days Day 15 only)			Cycle 2, Days 1 or 15 (± 2 days)		

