Screening/baseline tumor assessments should include CT or MRI of the chest and abdomen, pelvis, whole body bone scan, MRI of the brain and evaluation of any superficial lesions. For those sites that routinely use PET scans for assessment of bone lesions in lieu of skeletal scintigraphy, PET scans may be used on-study, with the same modality planned throughout the study for any given patient. CT or MRI of the chest, abdomen, and pelvis will be conducted at every subsequent assessment. Disease assessments subsequent to baseline assessment should also include whole body bone scans and/or MRI of the brain if metastatic disease is identified at screening/baseline by either the investigator OR the central radiology reviewer. Bone scans may be performed at one-half the frequency (every 12 weeks) of other disease assessments. All other suspected sites of disease should be evaluated at each assessment. Disease response will be assessed in accordance with RECIST 1.1 ([Eisenhauer-2009](#)). Appendix 2 provides guidance in using the response criteria and includes a modification to RECIST 1.1 to address potential temporary treatment effects such as tumor lesion cavitation. Assessments will be performed until objective disease progression is documented by the investigator, or subsequent anti-cancer therapy is begun.

Patients experiencing tumor response (Partial Response [PR] or Complete Response [CR]) should undergo confirmatory assessment at least 4 weeks after initial documentation of response. It is acceptable to perform confirmatory assessments at the next appointed evaluation per protocol. Bone scan is required as an element of the assessment of PR or CR response confirmation if bone lesions were identified at the baseline assessment. When bone scans are not protocol-specified, assessment for time point response will be based on assessment of all other lesions with imputation of Non-CR/Non-PD for bone lesions recorded as non-target lesions.

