9.9 Evaluation of Enrollment Stopping Rules

Disease response and progression as documented by the investigator in the CRF will be the basis for evaluation of the enrollment stopping rules. The following guidelines will apply to each treatment arm when determining number of events in the numerator and denominator in the stopping rules:

1. The numerator will include patients with objective responses (PR or CR) at any time prior to disease progression as assessed by the investigator and documented in the CRF. Unconfirmed responses will be included until sufficient time has elapsed to allow confirmation of response; if the response is not confirmed, the response will be excluded from the numerator during subsequent reviews.
2. The denominator will include:
 - a. Patients included in the numerator;
 - b. Patients discontinued from treatment;
 - c. Patients at the second or subsequent on-study disease assessment (scheduled after 4 treatment cycles, at Week 13) without PR, CR or PD (i.e., patient has Stable Disease [SD] or Not Evaluable [NE]).
3. The denominator will exclude:
 - a. Patients on treatment that have not yet reached the first on-study disease assessment;
 - b. Patients on treatment with SD or NE at the first on-study disease assessment (scheduled after 2 treatment cycles, at Week 7).

At each evaluation of stopping rules, the contribution of each participant's experience to the numerator or denominator will be updated based on current data. For example, a patient having SD at Week 13 may contribute only to the denominator at one evaluation, but be included also in the numerator at the next evaluation based on new data documenting PR or CR at Week 19.

A degree of discordance is expected between investigator assessments of disease response/progression and central review of disease response/progression. No attempt will be made to retrospectively apply the later emerging central review assessments to the enrollment stopping rules.

The IDMC may elect to apply the Bayesian Predictive Probability Design only to those patients taking the SDD formulation in order to mitigate the potential confounding effects from formulation change. These details are outlined in the IDMC charter.

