Potential exists for individual tumor lesions to develop necrosis, to cavitate, have a flair response to treatment or become otherwise difficult to evaluate for a period of time as the result of beneficial study treatment impact. For example, tumor necrosis, cavitation or flair may result in increase in overall size of individual lesions or unclear tumor margins prior to recovery to smaller lesions, development of scar tissue, or complete resolution. The true tumor measurements of lesions should be recorded but the conclusion of progressive disease may be suspended until continued assessment clarifies the nature of the tumor change. If repeat assessments indicate progression of disease, then PD should be recorded on the date of the first assessment giving the impression of progression. If repeat assessments indicate that the change was a process of transition, then NE (not evaluable) should be recorded during the period of transition, and PR or CR may be recorded for subsequent evaluations. The CRF will collect information on the observations during the period of transition to support the assessment conclusions.

Supplemental Investigations

If CR determination depends on a residual lesion that decreased in size but did not disappear completely, it is recommended the residual lesion be investigated with biopsy or fine needle aspirate. If no disease is identified, objective status is CR.

Best Objective Response

Target Lesions	Non-Target Lesions	New Lesion	Point in Time Response	Best Response
CR	CR	No	CR	CR and PR require confirmation at least 4 weeks after first observation
CR	Non-CR/Non-PD	No	PR	
PR	Non-PD	No	PR	
SD	Non-PD	No	SD	SD requires an on-study assessment after at least 6weeks on treatment. Unconfirmed PR or CR are reported as SD.
PD	Any	Yes or No	PD	
Any	PD	Yes or No	PD	
Any	Any	Yes	PD	

Subjective Progression

Patients requiring discontinuation of treatment due to worsening health status attributable to advancement of the malignancy under study but without objective evidence of disease progression should not be reported as PD on tumor assessment CRFs. This should be indicated on the end of treatment CRF as off treatment due to Global Deterioration of Health Status.

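### The 12-week cutoff for confirmed ORR falls before a second-scan response in the last patients dosed can be confirmed, so a response not yet confirmable counts as a non-response

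*Combined protocol and SAP*

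**What the plan says.** Section 9.4.1 defines ORR as the percentage of patients with a confirmed CR or PR on central review. It times the primary analysis at "approximately 12 weeks after the last patient is enrolled, allowing for observation of an early disease response and confirmation of PR or CR", and leaves other details to the SAP.

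The scan calendar starts at first dose, not at enrolment. Table 2, footnote 12 sets scans "every 6 weeks from dosing date [Cycle 1, Day 1] (-7/+10 days window allowed for first on-study assessment", with a window of ±10 days for later scans. Section 7.3 says that a responder "should undergo confirmatory assessment at least 4 weeks after initial documentation of response", and adds: "It is acceptable to perform confirmatory assessments at the next appointed evaluation per protocol".

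Appendix 2 supplies the default for a response without confirmation: "Unconfirmed PR or CR are reported as SD". Section 9.3.1 makes the analysis population "all patients who receive treatment at least one dose of MGCD265 on this study", so such a patient stays in the denominator.

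Section 9.9 treats pending responses differently for the enrolment stopping rules, which use investigator reads: "Unconfirmed responses will be included until sufficient time has elapsed to allow confirmation of response". It also gives an example of a patient with stable disease at Week 13 who is later "included also in the numerator at the next evaluation based on new data documenting PR or CR at Week 19".

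**The concern.** The endpoint requires confirmation, yet for the last patients dosed the cutoff comes before a scan-2 response can be confirmed. Under Appendix 2, a response that failed confirmation and one that has not had time to be confirmed receive the same label and both lower the ORR. Section 9.9 separates the two, but only for interim decisions. As supplied, the plan states no minimum follow-up, pending category or later update for the primary analysis.

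The anchor is also open. Section 9.4.1 does not say whether the last patient is the last in an arm, the last of an arm's first 45, or the last in the study including any expansion. The primary analysis in 9.1 is each arm's first 45 patients, so their follow-up depends on that reading.

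At stake is a modest understatement of ORR in whichever arm is still filling near the cutoff, with a read-out that depends partly on accrual timing.

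**Working it through.** **Dates.** Days are counted from first dose and compared with a cutoff of 12 × 7 = day 84, assuming dosing on the day of enrolment. Any delay from enrolment to dosing widens the gap.

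| Scan | Window (day) | Earliest confirmation (+28 days) | Next scheduled scan |
|---|---|---|---|
| 1 | 42 − 7 to 42 + 10 = 35 to 52 | 63 to 80 | 74 to 94 |
| 2 | 84 ± 10 = 74 to 94 | 102 to 122 (nominal 112) | 126 ± 10 = 116 to 136 |

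- Scan-1 response with a dedicated confirmatory scan: days 63-80, before the cutoff.
- Scan-1 response confirmed at scheduled scan 2: up to 94 − 84 = 10 days after it.
- Scan-2 response with a dedicated scan: at the earliest 102 − 84 = 18 days (2.6 weeks) after it; nominally 112 − 84 = 28 days (4.0 weeks).
- Scan-2 response confirmed at scan 3: nominally 126 − 84 = 42 days (6.0 weeks); at the latest 136 − 84 = 52 days (7.4 weeks).

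The patients exposed to the scan-2 gap are therefore those dosed in about the last 3-7 weeks before the analysed set closes. The word approximately would have to stretch by at least 18 days to remove it.

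**The plan's own figures.** An exact binomial recursion over the stopping boundaries in 9.1 (0/10 to 13/45) gives:
- type I error 0.0499 at a true ORR of 20%;
- power 0.9065 at 40%;
- early termination under the null 0.920;
- expected sample size 28.3.

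All match 9.1.

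**Illustration of size.** The documents give no accrual rate and no time-to-response distribution, so these inputs are assumed:
- the last k = 1 to 3 of an arm's 45 patients are exposed;
- each of their responses has a 20% or 40% chance of being lost from the final count;
- true ORR is 40% for power and 20% for type I error;
- central and investigator reads agree, and the interim looks keep the full investigator count.

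Expected responses lost = k × 0.4 × loss rate, from 1 × 0.4 × 0.2 = 0.08 to 3 × 0.4 × 0.4 = 0.48.

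| Exposed k | Power, at least 14/45 (20% / 40% lost) | Power, at least 15/45 (20% / 40% lost) |
|---|---|---|
| 0 | 0.9065 | 0.8507 |
| 1 | 0.9032 / 0.8999 | 0.8455 / 0.8403 |
| 2 | 0.8997 / 0.8927 | 0.8401 / 0.8292 |
| 3 | 0.8961 / 0.8848 | 0.8346 / 0.8175 |

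The first rule is the one in 9.1. The second is shown because the two-sided exact test in 9.4.1 needs 15 responses: 14/45 gives p = 0.090 and 15/45 gives p = 0.038.

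Type I error falls, from 0.0499 to between 0.0484 and 0.0411 at 14/45, and from 0.0245 to between 0.0236 and 0.0194 at 15/45.

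**The case against.** A reader might infer that the plan has no rule for a pending response. It does: Appendix 2 classes it as stable disease. The fault is narrower, in that the rule does not distinguish not yet confirmable from not confirmed.

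A reader might also infer that 9.4.1 contradicts itself. It promises only an early response and its confirmation, and a scan-1 response with a dedicated confirmatory scan meets that by day 80. What survives is that a scan-1 response confirmed at the next scheduled visit, which 7.3 allows, can miss day 84, and that a scan-2 response always does in the last patient dosed.

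Nor is 9.9 inconsistent with 9.4.1. It is an interim enrolment rule on investigator reads and may handle pending responses differently. It shows only that the sponsor already recognises the distinction.

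Two further objections stand. Section 9.4.1 defers details to the SAP, whose text was not available, so a rule there cannot be ruled out. And if the last patient means the last in the study, arms that fill early or are expanded already have longer follow-up, and the bias for them is near zero. For the same reason, a fix that started a separate 12-week clock in each arm could shorten their follow-up and should be avoided.

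**Conclusion.** The point holds in a limited form. Followed as written, the protocol counts a response that could not yet be confirmed as a non-response for patients dosed shortly before the analysed set closes. The dates rest only on the scan schedule and confirmation interval, plus the reading of 12 weeks as about day 84.

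The bias is downward and conservative. It does not inflate type I error, and the investigator-based stopping rules are untouched. The loss of 0.3 to 2.2 percentage points of power under the 9.1 rule (0.9065 − 0.9032 = 0.0033; 0.9065 − 0.8848 = 0.0217) is an illustration on assumed inputs, not an estimate. The design has little room, since 9.1 requires power of at least 0.90, but the documents do not support a claim that the trial is materially underpowered for this reason. This is a point for the sponsor to consider.

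**What to change.** If the SAP does not already cover it, add to 9.4.1:

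*A response seen by central review at or before the cutoff and still awaiting confirmation is resolved by its confirmatory (or next scheduled) scan before the primary ORR is finalised; if disease assessments have stopped, it counts as unconfirmed.*

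Also state that the cutoff is no earlier than 94 days after the first dose of the last patient in each arm's primary analysis set. This is a minimum follow-up only and must not bring forward the read-out of any arm. It covers the full scan-2 window and settles what the last patient means for the minimum. Alone it does not close the scan-2 gap, since day 94 is before day 102; the first sentence does that.

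Cost: the minimum delays the read-out by up to 94 − 84 = 10 days, plus any lag from enrolment to dosing. Resolving a pending response takes the read-out about 4-6 weeks beyond day 84 on the nominal schedule (2.6-7.4 weeks across the windows), and only if one is pending. No patients or procedures are added. Responses first seen at Week 19 in the last patients remain outside this change; capturing them would need longer follow-up.
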